3.2.5 Follow-up (FU) Visit

3.2.5.1 Visit 8 (Week 17, Day 120 \pm 3 days)

A post-treatment Follow-up Visit will occur 14 \pm 3 days after completion of the treatment period. Subjects will report to the clinic in the morning where the following activities will be performed:

- Review of concomitant medications and supplements.
- Physical examination will be performed.
- Urine pregnancy test will be performed.
- Measurement of vital signs (SBP/DBP and heart rate).
- AEs will be recorded.
- Subjects will be discharged from the study.

3.2.6 Unscheduled (UNS) Visit

Should there be a need for an unscheduled (UNS) visit, (e.g., to manage or Follow-up on unresolved AEs), the investigator will use their judgment and perform an adequate evaluation of the subject. Prior and concomitant medications and supplements, vital signs, physical examination, weight, adverse events assessment, and clinical lab tests will be performed as necessary and data will be recorded.

3.3 Schedule of Events

[Table 1](#) presents the schedule of events for all study visits.

Table 1. Schedule of Events

| Study Period | SCR | BSL | | | | | | | | |
|-------------------------------------------------------|-----------|----------------|----------------|-----------------|-----------------|------------------|------------------|-------------------|-------------------|-----|
| Visit | S | 1 | 2 | 3 | 4 | 5 | 6 | EOS/ET [7] 7 | FU 8 | UNS |
| Study Week | | 0 | 1 | 2 | 3 | 7 | 11 | 15 | 17 | |
| Study Day [1] | -28 to -1 | 1 (± 1 day) | 8 (± 1 day) | 15 (± 1 day) | 22 (± 1 day) | 50 (± 3 days) | 78 (± 3 days) | 106 (± 3 days) | 120 (± 3 days) | |
| Informed Consent Form | X | | | | | | | | | |
| Eligibility Criteria | X | X ^a | X ^a | X ^a | X ^a | X ^a | X ^a | | | |
| Demographic Data (sex, DOB, race, and ethnicity) | X | | | | | | | | | |
| Medical History (including tobacco and alcohol use) | X | | | | | | | | | |
| Prior and Concomitant Medications and Supplements [2] | X | X | X | X | X | X | X | X | X | X |
| Physical Examination [3] | X | X ^a | | | X | X | X | X | X | X |
| Height and Weight [4] | X | X | | | X | X | X | X | | X |
| PASI, BSA and IGA | X | X ^a | X | | X | X | X | X | | |
| DLQI | X | X ^a | | | X | X | X | X | | |
| I-NRS | | X | | | X | | | X | | |
| Vital Signs [4] | X | X ^a | X | X | X | X | X | X | X | X |
| Pregnancy Test [5] | X | X ^a | | | X ^a | X ^a | X ^a | X | X | |
| Blood Sample for Immunogenicity Assessment | | X ^a | | | X ^a | | | X | | |
| Blood Sample for PK assessment | | X ^a | X ^a | X ^a | X ^a | X ^a | X ^a | | | |
| Blood Sample for Clinical Lab Tests [#] | X | X ^a | | | X ^a | | | X | | X |
| Serology (Hepatitis B and C, and HIV) | X | | | | | | | | | |
| Exploratory Biomarkers [6] | | X ^a | X ^a | X ^a | X ^a | X ^a | X ^a | X | | |
| CCTA | X | | | | | | | X | | |
| Randomization | | X ^a | | | | | | | | |
| IV Administration | | X | X | X | X | X | X | | | |
| Adverse Events | | X [^] | X | X | X | X | X | X | X | X |

Table 1 Footnotes

BSL = Baseline; DOB = Date of Birth; CCTA = Coronary Computed Tomography Angiography; EOS = End of Study; ET = Early Termination; FU = Follow-up; UNS = Unscheduled; PASI = Psoriasis Area and Severity Index; IGA = Investigator Global Assessment; BSA = Body Surface Area; DLQI = Dermatology Life Quality Index; I-NRS = Itch Numerical Rating Scale; PK = Pharmacokinetic; IV = Intravenous

^aAssessment to be performed/samples to be collected prior to dosing.

[1] For Study Weeks 1-15: Clinic visits should occur within ± 1 days. Follow-up Visit should occur within ± 3 days.

[2] Prior and concomitant medications and supplements will be reviewed at Screening, Early Termination (ET) Visit (if applicable), and Unscheduled (UNS) Visit (if applicable). Concomitant medications and supplements will be reviewed as indicated.

[3] Physical examination will include the following organ or body system assessments: general appearance; eyes; ears, nose, and throat; head and neck; chest and lungs; cardiovascular; abdomen; musculoskeletal; lymphatic; dermatological; neurological; and extremities.

[4] Heart rate and blood pressure.

[5] Serum pregnancy test at Screening, urine pregnancy test at Visits 1, 4, 5, 6, 7, and FU Visit.

[6] See Efficacy Assessment Section under “[Cardiometabolic and Inflammatory Biomarkers](#)”.

[7] Subjects withdrawing prematurely from the trial at any visit will have the ET visit procedures completed.

[\$] Height and weight will be measured at Screening and weight will be measured at Weeks 0, 3, 7, 11, 15, and Unscheduled (UNS) Visit (if applicable).

[#] Clinical lab tests will include hematology, serum chemistry (includes a standard lipid panel), and coagulation parameters (includes an activated partial thromboplastin time (aPTT) test).

[^] AE's will only be collected after dosing on Visit 1 (Week 0).

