3.2.4 End of Study/Early Termination Visit (EOS/ET Visit)

3.2.4.1 Visit 7 (Week 15, Day 106 ± 3 days)/ ET Visit

Subjects will report to the clinic in the morning following a 10-hour fast where the following activities will be performed:

- Collection of fasted blood samples for (see [Section 6.3.2](#) for a list of tests):
 - Clinical laboratory tests (including urine pregnancy test for females, biomarkers test, and aPTT test).
 - Immunogenicity testing.
- Review of concomitant medications and supplements.
- Physical examination will be performed.
- IGA will be performed.
- PASI Score will be evaluated.
- BSA will be measured.
- DLQI questionnaire will be completed.
- I-NRS questionnaire will be completed.
- Measurement of vital signs (SBP/DBP and heart rate).
- Weight will be measured.

- CCTA will be performed.
- AEs will be recorded.
- Subjects will be instructed to return to the clinic in 2 weeks for Follow-up Visit 8 (or discharged from the study if terminated early).

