 16. Has an underlying condition that predisposes to infections (e.g. immunodeficiency, HIV, or splenectomy).
 17. Chronic or acute hepatitis B and C, or carrier status.
 18. History of tuberculosis, tuberculosis or a positive tuberculin skin test (TST) for tuberculosis. Participants who previously received BCG vaccination can participate in the study after showing negative responses in Interferon-Gamma Release Assays (IGRA).
 19. History of malignancy in the past 5 years or suspicion of active malignant disease except treated cutaneous squamous cell or basal cell carcinoma and treated carcinoma in situ of the cervix uteri.
 20. Diagnosis of major depressive disorder, schizophrenia, bipolar disorder, personality disorder or other DSM-V disorders which the investigator believes will interfere significantly with study compliance.
 21. A history of any clinically important abnormalities in cardiac rhythm or conduction.
 22. A history of prolonged QT intervals or a family history of long QT-syndrome at Screening.
 23. A history of first, second or third-degree atrioventricular (AV) block, or AV dissociation.
 24. A history of complete bundle branch block.
 25. Unstable angina pectoris, myocardial infarction, transient ischemic attack, or stroke within 3 months prior to Screening, or participants who have undergone percutaneous coronary intervention or a coronary artery bypass graft within 6 months prior to Screening or who are due to undergo these procedures at the time of Screening.
 26. Severe congestive heart failure (NYHA III or IV).
 27. Prior history of contrast-induced nephropathy.
 28. Known or suspected allergy to iodinated x-ray contrast.
 29. Estimated GFR < 60 mL/min/1.73 m² {MDRD formula}.
 30. Contraindications to intravenous metoprolol (beta adrenergic blocker) during CCTA imaging procedure.
 31. Contraindications to sublingual nitroglycerine during CCTA imaging procedure.

32. Subject is a user of recreational or illicit drugs or has had a recent history (within 1 year of Screening) of drug or alcohol abuse or dependence. (Note: Alcohol abuse includes heavy alcohol intake as defined by >3 drinks per day or >14 drinks per week, or binge drinking) at Screening. Occasional intermittent use of cannabinoid products will be allowed provided that no cannabinoid products have been used during the 1 week prior to each visit.

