4.4 Removal of Subjects from Therapy or Assessment

Subjects may choose to withdraw from this study at any time for any reason without penalty of jeopardizing their health care or loss of benefits to which the subject is otherwise entitled.

Within the provisions of informed consent and good clinical judgment with respect to safety, every attempt will be made to have subjects complete the study. Reasons for subject discontinuation include, but are not limited to the following:

1. Subject experiences an AE that in the judgement of the Investigator poses a significant risk to the subject for continued participation in the study.
2. Subject uses a prohibited medication (listed in [Section 5.9.2](#)) that in the judgment of the Investigator poses a significant risk to the subject for continued participation in the study or that will interfere with the interpretation of the results of the study.
3. Subject becomes pregnant.
4. Significant protocol violation or noncompliance on the part of the subject or the Investigator.
5. Intercurrent illness requires treatment not consistent with the protocol requirements, or intercurrent illness and the associated treatment poses a significant risk to the subject for continued participation in the study in the judgment of the Investigator.
6. Subject meets one of the exclusion criteria during the study.
7. Subject wishes to withdraw for any reason.
8. Sponsor elects to end the study or the Investigational Site elects to end the study at their site.
9. Any other reason that in the judgment of the Investigator poses unacceptable risk to the subject.

Subjects who withdraw from the study prior to treatment may be replaced. Subjects who are withdrawn and have received at least one treatment will not be replaced.

Except in cases of emergency, the Investigator should consult with the Sponsor and the Medical Monitor before removing the subject from the study. In some circumstances, it may be necessary to temporarily interrupt treatment because of AEs that may have an unclear relationship to study treatment. The Investigator should obtain approval from the Sponsor and Medical Monitor before restarting study treatments that were temporarily discontinued for an AE.

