If a subject discontinues the study prior to completion, the date the subject is withdrawn and the reason for discontinuation will be recorded in the source documents and eCRF. Although a subject will not be obliged to give his/her reason for withdrawing prematurely, the Investigator will make a reasonable effort to obtain the reason while fully respecting the subject's rights.

All subjects who are randomized and treated (i.e., received any amount of study treatment) will be included in the safety analyses. Thus, every effort will be made to contact any subject who fails to attend any Follow-up appointments/contacts, to ensure that he/she is in satisfactory health. If a subject withdraws from the study as a result of meeting discontinuation criteria (Section 4.4) after the start of study treatment administration, reasonable efforts should be made to have the subject return for the early termination evaluations (Section 3.2.4). Any subject withdrawn due to a suspected study treatment-related AE should be followed until resolution or stabilization of the event.

If a subject becomes pregnant, study treatment will be discontinued immediately. The subject will be followed until delivery or other termination of pregnancy for outcome.

The Sponsor has the right to terminate this study, and the Investigator/Investigational Site has the right to close the site, at any time, although this should occur only after consultation among involved parties. The Investigator will notify the IRB in writing of a premature termination of a study or closure of Investigational Site and will send a copy of the notification to the Sponsor.

Events that may trigger premature termination of a study or closure of an Investigational Site include, but are not limited to, a new toxicity finding, a request to discontinue the trial from a regulatory authority, non-compliance with the protocol, GCP violations, slow recruitment/low enrollment, or change in development plans for the study treatment.

Enrollment of new subjects and dosing of ongoing subjects will be temporarily stopped based on the stopping criteria (See Section 12.2). The Investigator, Sponsor, and the Medical Monitor will discuss whether a lower dose or any additional treatment guidelines should be implemented, or if the trial should be permanently stopped. Any proposed changes to the protocol to address such findings will be submitted for review and approval by the IRB and FDA prior to re-starting the trial.

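### A subject withdrawn for pregnancy or eGFR < 60 is directed to an early-termination visit that lists contrast CCTA, with no exception

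*Protocol*

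**What the plan says.** Coronary CT angiography is scheduled twice: at Screening, and in the combined Visit 7 (Week 15)/early-termination column of Table 1. For that second visit Protocol Section 3.2.4.1 states "CCTA will be performed". Neither that line nor the Table 1 CCTA row carries a condition or footnote.

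Two texts send early leavers to this visit. Table 1 footnote [7] is unqualified: "Subjects withdrawing prematurely from the trial at any visit will have the ET visit procedures completed". Section 4.4 is softer. For subjects who meet discontinuation criteria after treatment has started, it says "reasonable efforts should be made to have the subject return for the early termination evaluations".

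The discontinuation reasons in Section 4.4 include "Subject becomes pregnant" (reason 3) and "Subject meets one of the exclusion criteria during the study" (reason 6). The exclusions in Section 4.3 include pregnancy or breastfeeding (15), earlier contrast nephropathy (27), "Known or suspected allergy to iodinated x-ray contrast" (28), eGFR below 60 (29), and contraindications to the metoprolol and nitroglycerine used in the imaging procedure (30 and 31).

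**The concern.** Meeting one of these exclusions on study is a reason to withdraw the subject. Withdrawal triggers the early-termination visit, and that visit lists contrast CCTA. The protocol therefore treats a condition as a reason not to take part, then directs the subject who develops it to the contrast procedure.

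At stake is the safety of the few subjects concerned and the clarity of the instruction to sites. No efficacy conclusion depends on it, because all CCTA endpoints are exploratory.

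**Working it through.** The plan states no figure on this point, so the check is to trace the text. Two short calculations then give the scale.

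**Chain of instructions**

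| Step | Source | Content |
|---|---|---|
| 1 | Protocol 4.3 | Exclusions 15 and 27-31 |
| 2 | Table 1, eligibility row | Marked at Screening and pre-dose at Visits 1-6: "Eligibility Criteria | X | X ^a | X ^a | X ^a | X ^a | X ^a | X ^a". Blank at Visit 7/ET |
| 3 | Protocol 4.4, reasons 3 and 6 | Pregnancy, or any exclusion met on study, is a reason to discontinue |
| 4 | Table 1 footnote [7]; Protocol 4.4 | Early leavers have the ET procedures (footnote), or the site tries to bring them back for these (4.4) |
| 5 | Protocol 3.2.4.1; Table 1, CCTA row | CCTA is one of those procedures, without condition |

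**Search for an exemption.** None was found.
- The pregnancy paragraph of Section 4.4 stops treatment and follows the pregnancy, but does not mention the scan.
- Section 5.9.2 sets two medication limits around CCTA (phosphodiesterase inhibitors before, metformin after). It says nothing on pregnancy, renal function or contrast history.
- Sections 6.5.3 and 6.5.4, and SAP 2.9.7, describe only the measurements and their analysis.

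**Two routes through the text**
- Pregnancy: urine tests are scheduled before dosing at Visits 4, 5 and 6. A positive result leads to reason 3, then the ET visit, then CCTA.
- Low eGFR: chemistry, which includes creatinine, is drawn at Visits 1 and 4 and sent to a central laboratory (Section 6.3.2). If the result returns after that day's dose, an eGFR below 60 leads to reason 6, then the ET visit, then CCTA. The turnaround time is not stated, so a late result is an assumption.

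**Subjects who reach Week 15.** A urine pregnancy test and a chemistry sample are listed at Visit 7, but no sentence makes the scan depend on either, and no order is set. The previous scheduled chemistry is Visit 4:
- Nominal gap: 106 − 22 = 84 days.
- With the windows in the Table 1 columns (±1 and ±3 days): shortest (106 − 3) − (22 + 1) = 80 days; longest (106 + 3) − (22 − 1) = 88 days.

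**Scale.** Section 4.1 enrols about 75 so that at least 60 complete: 75 − 60 = 15, and 15/75 = 20%. This is the planning ceiling for early withdrawal for any reason. The documents do not say how many would leave for pregnancy or low eGFR.

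**The case against.** The strongest reply is that no competent site would do the scan. Section 4.4 puts its effort to keep subjects in the study under good clinical judgement on safety, and asks only for a reasonable attempt to bring them back. Section 11.2.3 allows a departure without prior IRB approval to remove an immediate hazard. On this view footnote [7] is a generic rule that lacks an exception.

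Part of that stands: a careful site would probably omit the scan. But the judgement clause concerns completing the study and does not mention CCTA. Section 11.5 also requires the protocol to be implemented as written, with written medical-monitor approval for deviations. The safe outcome would depend on a deviation.

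A reader might also infer stronger points that the documents do not support:
- *The exclusions stop operating after the first scan.* They do not. They are reviewed before dosing up to Visit 6 and are grounds for discontinuation. The gap is that nothing applies them to the second scan.
- *A reaction to the Screening contrast leads to a second scan.* Ordinarily it would not. Sections 3.2.2, 3.2.3.1 and 5.9.1 apply the criteria through Day 1, so that subject would be a screen failure. No study contrast is given between then and Visit 7/ET, so a new contrast allergy would ordinarily need exposure outside the study.
- *An 84-day-old renal result is itself an error.* The documents set no maximum age, and unscheduled laboratory tests are allowed. The interval only shows that no scheduled result fills the gap.
- *Fifteen subjects are affected.* That figure covers every reason for leaving.

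**Conclusion.** The point holds in a limited form. The early-termination instruction conflicts with the protocol's own exclusions for a subject withdrawn because of pregnancy or eGFR below 60. It is a stated rule with a safety consequence, which is more than missing detail. The number of such subjects is unknown and probably small, but the conflict arises in every such case.

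The conclusion rests on reading footnote [7] as written, and on taking exclusions 15 and 29 to be relevant to contrast CT. Neither criterion names the scan, although 29 stands among exclusions that concern contrast and CCTA. For subjects who reach Week 15 the finding is narrower: the scan is not linked to any check of these criteria at that visit.

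**What to change.** The sponsor should reconcile Table 1 footnote [7], Section 3.2.4.1, the Table 1 CCTA row and Section 4.4 with exclusions 15 and 27-31, so that the ET instruction no longer conflicts with the protocol's own CCTA-related exclusions. The same revision should make clear how those exclusions bear on the Visit 7 scan. Under what clinical conditions a second scan may be done, and on which results, is for the sponsor's clinicians; none is proposed here.

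The cost is protocol wording and the possible loss of a few ET scans taken before Week 15. The CCTA endpoints are exploratory and defined as change at Week 15 (Protocol Section 2, SAP 1.3.6), and SAP 2.9.7 does not say how an earlier ET scan would be used.

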4 STUDY SUBJECT SELECTION AND WITHDRAWAL CRITERIA

4.1 Number of Subjects

Approximately 75 subjects will be enrolled in at least 17 sites in the US to ensure that at least 60 subjects complete the study. Subjects will be randomized in a 2:1 ratio, orticumab to placebo. Subjects who discontinue prematurely will not be replaced.

4.2 Inclusion Criteria

Subjects may be enrolled if the following criteria are met:

1. Stable/chronic plaque psoriasis with PASI score of ≥ 12 AND involving $\geq 10\%$ of the subject's BSA.
2. Males and Females ≥ 30 years of age at time of consent.
3. Females of childbearing age must use 2 forms of birth control.
4. BMI ≥ 30 kg/m².
5. LDL ≥ 100 mg/dL at Screening.
6. All females must have a negative serum pregnancy test result at Screening and a negative urine pregnancy test at Day 1 (Visit 1) prior to dosing.

4.3 Exclusion Criteria

Subjects are excluded from the study if any of the following criteria are met:

1. Past use of orticumab.
2. Any of the nonplaque forms of psoriasis: erythrodermic, guttate, or pustular.
3. Scalp, palmar or plantar psoriasis only, at Screening or Baseline.
4. Have evidence of skin conditions (e.g., eczema) at the time of Screening or Baseline visit that would interfere with the evaluation of psoriasis.
5. Newly discovered Type 2 diabetes mellitus (T2DM) within 90 days of Screening (prior to study entry) or medical treatment for T2DM started < 90 days prior to Screening.
6. Moderate or high-intensity statin use or new use of a low-intensity statin therapy within 90 days of Screening. Low-intensity statin therapy is permitted provided it is limited to lovastatin, fluvastatin, pravastatin ≤ 40 mg daily, simvastatin ≤ 20 mg daily, or pitavastatin ≤ 2 mg daily AND the dose has remained stable and unchanged for ≥ 90 days prior to the screening visit and NO DOSE change is anticipated for the approximate 20-week duration of the trial. See [Section 5.9.2 Prohibited Medication](#). No other non-statin lipid-modifying therapy is permitted.
7. No use of anti-coagulating agents or anti-thrombotic agents within 90 days prior to the Screening visit. Low dose aspirin limited to ≤ 81 mg daily provided the dose has remained stable and unchanged for ≥ 90 days prior to the Screening visit. Nonsteroidal anti-inflammatory drugs are not permitted for the duration of the trial from the Screening Visit.
8. Poorly controlled hypertension defined as:
 - a. Systolic blood pressure (BP) > 160 mm Hg.

-
- b. Diastolic BP > 90 mm Hg.
9. Antihypertensive medication is permitted provided it is limited to two or less medications and all have been stable and unchanged for ≥ 90 days prior to the screening visit and NO DOSE change is anticipated for the approximate 20-week duration of the trial.
 10. Use of topical therapies, phototherapy (UVA or UVB) or tanning salons for the treatment of psoriasis in the past 4 weeks.
 11. Use of an IL-23 blocker in the past 180 days, an IL-17 blocker in the past 16 weeks, or a TNF blocker in the past 12 weeks.
 12. Use of methotrexate, cyclosporine, or apremilast in the past 4 weeks.
 13. History of hypersensitivity or allergies to any contents in the orticumab formulation.
 14. Participation in any clinical study with an investigational drug/device within 4 weeks prior to the first day of dosing.
 15. Is pregnant or breastfeeding.
 16. Has an underlying condition that predisposes to infections (e.g. immunodeficiency, HIV, or splenectomy).
 17. Chronic or acute hepatitis B and C, or carrier status.
 18. History of tuberculosis, tuberculosis or a positive tuberculin skin test (TST) for tuberculosis. Participants who previously received BCG vaccination can participate in the study after showing negative responses in Interferon-Gamma Release Assays (IGRA).
 19. History of malignancy in the past 5 years or suspicion of active malignant disease except treated cutaneous squamous cell or basal cell carcinoma and treated carcinoma in situ of the cervix uteri.
 20. Diagnosis of major depressive disorder, schizophrenia, bipolar disorder, personality disorder or other DSM-V disorders which the investigator believes will interfere significantly with study compliance.
 21. A history of any clinically important abnormalities in cardiac rhythm or conduction.
 22. A history of prolonged QT intervals or a family history of long QT-syndrome at Screening.
 23. A history of first, second or third-degree atrioventricular (AV) block, or AV dissociation.
 24. A history of complete bundle branch block.
 25. Unstable angina pectoris, myocardial infarction, transient ischemic attack, or stroke within 3 months prior to Screening, or participants who have undergone percutaneous coronary intervention or a coronary artery bypass graft within 6 months prior to Screening or who are due to undergo these procedures at the time of Screening.
 26. Severe congestive heart failure (NYHA III or IV).
 27. Prior history of contrast-induced nephropathy.
 28. Known or suspected allergy to iodinated x-ray contrast.
 29. Estimated GFR < 60 mL/min/1.73 m² {MDRD formula}.
 30. Contraindications to intravenous metoprolol (beta adrenergic blocker) during CCTA imaging procedure.
 31. Contraindications to sublingual nitroglycerine during CCTA imaging procedure.

32. Subject is a user of recreational or illicit drugs or has had a recent history (within 1 year of Screening) of drug or alcohol abuse or dependence. (Note: Alcohol abuse includes heavy alcohol intake as defined by >3 drinks per day or >14 drinks per week, or binge drinking) at Screening. Occasional intermittent use of cannabinoid products will be allowed provided that no cannabinoid products have been used during the 1 week prior to each visit.

